Missing Data: Participants who do not submit data at F1 or who decline navigation will continue to be contacted at F2 to complete questionnaires (unless they withdraw from the study) for intent to treat analyses. We plan to begin recruitment early in the care trajectory and anticipate most patients will survive the 8-week study period and will be able to provide the limited amount of data we are collecting. The median survival time for patients with primary malignant brain tumor is 14.6 months.(National Brain Tumor Society) In the unlikely event patients no longer receive care in the neuro-oncology clinic at Moffitt (transition to palliative/hospice care, change providers, death) participants will not be dropped (unless they request to withdraw). Participants in the intervention condition will still have access to eSNAP (and the Navigator) if they wish, with the intent of allowing FCGs to use the intervention to help cope with the new phase of caregiving or bereavement. FCGs will still be asked to complete follow-up questionnaires. If a patient dies, the date of death will be noted, a bereavement card will be sent from the study team, and an abbreviated version of any further surveys will be administered focused on key outcome data for exploratory purposes.

Sample size justification: The analyses for Aims 1 & 2 focus on group differences in parametric variables. A power analysis for an independent-groups t-test with a medium effect size (Cohen's $d=0.5$) shows that a final sample of 160 (80 per group) would have Power $\geq .80$ with alpha=.05 and a two-tailed test. Based on our conservative recruitment and retention estimates, we plan to approach 300 FCGs and enroll 225 to achieve a final sample of 160 dyads completing the 8-week assessment for analyses of hypotheses. However, as the planned recruitment/retention rates are lower than what we achieved in our pilot, we may have a larger sample at F2, which will increase our power. Analyses for exploratory Aim 3 will

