primarily use path analysis to identify key mechanisms of the intervention on the outcome variable(s) at the 4- and 8-week assessment among the FCGs. The 80 participants in the intervention group will provide the primary data for these analyses, with additional data from participants in the waitlist control group who complete these assessments. It is expected that at least 50% in this group will provide data. Therefore, the expected sample size for the exploratory analyses will be at least 120.

Preliminary analysis: Basic descriptive analyses will be conducted. Chi-square and t-tests will be conducted to determine if the intervention (eSNAP + Caregiver Navigator; both randomized and non-randomized groups) or waitlist control groups significantly differ on demographics, patient medical characteristics, or outcome measures at baseline. Any measure with a group differences of $p < .10$ will be controlled for in primary analyses. Group differences and predictors of attrition will be examined using logistic regression. These results will be used to guide interpretation of primary analyses.

Aim 1 is to assess the preliminary efficacy of eSNAP + Navigator support intervention on FCG well-being. The hypothesis (FCG burden and distress at 8 weeks is lower for intervention group) can be most simply evaluated using independent-samples t-tests if randomization is fully successful. However, Generalized Estimating Equations (GEE) will be used to test the effects of the intervention at F1 and F2 in models that also include the baseline measure of the outcome variable and, if necessary, potential confounds determined by preliminary analyses. This approach handles missing data under the Missing At Random (MAR) assumption and permits analyses beyond those focusing on the outcome variable at 8 weeks (e.g. determining if intervention has an early impact or if effect matures over time). The primary test will be a planned contrast of the 2 conditions at the 8-week assessment within the entire model. The GEE will also assess (1) intervention differences in the primary outcome averaged across the 4 and 8 week assessments, (2) change from 4 to 8 weeks, and (3) group differences in change over time (intervention by time interaction term in the model).

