Aim 2 is to assess the preliminary efficacy of interdependent effects of eSNAP + Navigator on patient well-being and health care utilization. We hypothesize that patients with FCGs in the intervention group will report greater well-being and less utilization of health care. The primary outcomes for this aim are (1) patient anxiety and depression scores as (inverse) measures of well-being, and (2) a set of measures for healthcare utilization: the presence of and number of unplanned outpatient visits, the presence of and number of unplanned hospitalizations, and the number of bed days of care in unplanned hospitalizations. For well-being, the simplest test of the hypothesis is an independent samples t-test. If preliminary analyses show that randomization was not fully successful, then linear regression will be used to assess differences between the intervention arms in the context of any potential confounds. For healthcare utilization, the distributions of the outcome variables are expected to warrant 2-stage and/or Poisson regression analyses to assess intervention differences.

Exploratory Aim 3 is to identify key intervention components using mixed methods to inform future intervention implementation. Our quantitative approach will first involve determining the **timing and dose effects of the intervention**. Between-groups GEE analyses will utilize the full dataset to determine if stronger effects of the intervention exist when the intervention is delivered at the first treatment planning appointment (intervention group) or 8 weeks later (waitlist participants who engage in the intervention). We will also analyze data collected from all participants at 6 months and 1 year. Although likely a smaller dataset with some selection bias, these data may provide insight into long term effects on FCG and patient well-being and an opportunity to capture patient hospitalization, a relatively rare but important downstream effect of FCG burden.

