Qualitative analysis of FCG interviews will augment quantitative analysis. FCGs will be interviewed at 8 weeks about their caregiving experience, including what they liked about the intervention and what could be improved (See Appendix for draft interview guide). Interview audio recordings will be professionally transcribed verbatim. Transcripts will undergo content analysis using open and axial coding by 2 trained coders, led by [name], who has expertise in qualitative analysis.(Dingley et al., 2017; Ellington et al., 2017; Lai et al., 2018; Reblin, Birmingham, Kohlmann, & Graff, 2018; Reblin et al., 2015; Tabler et al., 2015) The goal of the analysis will be to identify aspects of the intervention FCGs found helpful and areas for improvement. Deeper analysis on select transcripts will be conducted to identify themes relevant to findings of the quantitative analysis and emergent themes regarding the caregiving experience.

The audio recordings and transcripts will be stored on secure, password-protected computer servers and will only be accessed by study team members. Audio recordings and transcripts will be retained for at least six years after the study is completed, after which they will be deleted from computer records.

5. Human Subjects Protection

Potential Risks:

There are a few potential risks to the participants. Participants may feel emotional distress when completing questionnaires or thinking about their social networks or caregiving experiences. There is also the possibility of loss of privacy or confidentiality.

Planned strategies for minimizing potential risks

Emotional Distress:

Participants may feel emotional distress when completing questionnaires or thinking about their social networks or caregiving experiences. Some participants may become distressed as a result of their experiences in caregiving. This level of distress is not likely to be more than would occur in daily life or as part of usual care. In the intervention condition (which waitlist control participants may receive after 8 weeks), the Caregiver Navigator will have training to counsel or refer any participant who feels distressed,

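### The exploratory timing contrast defines early delivery by assigned group but delayed delivery by engagement, so it carries selection in one arm; the Aim 3 sample of at least 120 also needs restating

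*Combined protocol and SAP*

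**What the plan says.** Section 4 (Exploratory Aim 3) sets out a comparison of early with delayed delivery. The early side is the intervention group, named without any restriction to those who engaged. The delayed side is delivery "8 weeks later (waitlist participants who engage in the intervention"). On the data to be used, the section says: "Between-groups GEE analyses will utilize the full dataset".

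Three other places bear on who falls on each side:

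- Uptake by the waitlist is optional. Section 5 (Emotional Distress) speaks of the intervention condition as one "In the intervention condition (which waitlist control participants may receive after 8 weeks"); the operative word is may.
- Intervention caregivers who decline part of the intervention are kept. Section 4 (Missing Data) provides: "Participants who do not submit data at F1 or who decline navigation will continue to be contacted at F2 to complete questionnaires", for intent-to-treat analyses.
- Section 4 (dosing paragraph of Aim 3) hypothesises that caregivers with less support, or with more distress or burden at enrollment, will use more of the intervention's components.

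On sample size, Section 4 (Sample size justification) counts 80 intervention participants for Aim 3, which will rest mainly on path analysis, and says of the waitlist: "It is expected that at least 50% in this group will provide data". It concludes that "the expected sample size for the exploratory analyses will be at least 120".

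**The concern.** Randomisation makes the two groups comparable as assigned. It does not make one whole group comparable with the self-selected part of the other. Here the filter is applied on the delayed side only, and by the plan's own hypothesis it works on need, which is closely tied to burden and distress, the caregiver outcomes.

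Nothing elsewhere in the plan repairs this. The remark about some selection bias is attached to the 6-month and 1-year data. Adjustment for baseline score and confounders is specified for Aim 1, not for the timing contrast. No engagement definition, weighting or all-offered comparison is given.

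Aim 3 is meant to inform future implementation, and timing is its first quantitative question. A difference between early and delayed delivery could be read as advice on when to deliver the intervention when part of it reflects who took up a delayed offer. The plan's expected Aim 3 sample also still assumes two groups of 80, which the modified design no longer provides.

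**Working it through.** **1. The two sides of the contrast**

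| | Early delivery | Delayed delivery |
|---|---|---|
| Defined by | Group | Engagement after the 8-week wait |
| Caregivers who decline navigation | Followed and kept | No rule stated |
| Non-randomised caregivers (after amendment V11) | Pooled into the intervention group in the preliminary analysis | None |

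The last row is a second, separate source of non-comparability.

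**2. Possible size of the selection effect (illustration)**

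The documents give neither the share that will engage (f) nor the correlation of engagement with outcome (r); both are assumed. If engagement propensity and outcome are bivariate normal and the share f with the highest propensity engages, the mean outcome of engagers shifts by r × φ(c)/f SD, where c = Φ⁻¹(1 − f).

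| Share engaging | φ(c)/f | r = 0.1 | r = 0.2 | r = 0.3 | r = 0.5 |
|---|---|---|---|---|---|
| 50% | 0.798 | 0.08 | 0.16 | 0.24 | 0.40 |
| 75% | 0.424 | 0.04 | 0.08 | 0.13 | 0.21 |
| 90% | 0.195 | 0.02 | 0.04 | 0.06 | 0.10 |

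These shifts are before any adjustment. With no true timing effect and half the waitlist engaging, the two-sided 5% error rate of a t-test at 80 versus 40 becomes about 7%, 13%, 23% and 53% for r = 0.1, 0.2, 0.3 and 0.5. At sizes nearer the modified design (107 × 0.85 ≈ 91 versus 53 × 0.85 × 0.5 ≈ 23) it is about 6%, 10%, 17% and 40%.

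A comparison of everyone as randomised, with all outcomes observed, has no such shift and keeps the rate near 5%.

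**3. The Aim 3 sample**

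- The plan's figure reproduces: 80 + 0.50 × 80 = 120. It needs the equal-group design.
- Modified design (Sections 3a and 3b): 160 enrolled at about 2:1 gives about 107 intervention and 53 waitlist.
- Waitlist contribution at 50%: 0.50 × 53 = 26.5. The 50% is a data-provision rate, so no further attrition is taken from it.
- Intervention group with 15% attrition applied once: 107 × 0.85 = 91.0; total 91.0 + 26.5 ≈ 117.
- Applied twice, as the plan's wording of 15% at each follow-up implies for week 8: 107 × 0.7225 = 77.3; total 77.3 + 26.5 ≈ 104.
- With no intervention-group attrition: 107 + 26.5 ≈ 133. Under the plan's own 15%, the stated minimum is not reached at a 50% waitlist contribution.

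**The case against.** The strongest reply is that the analysis is said to use the full dataset. The parenthesis may only describe who receives delayed delivery, without removing anyone's records. That ambiguity is real and the authors should resolve it. It does not cure the problem: even with every record in the model, delayed exposure is still identified by engagement and early exposure by group.

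Several further objections stand and limit the point:

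- A reader might infer that the timing estimate would mainly reflect who engages. The documents do not support that. Both f and r are assumed, and with high uptake the shift is small. The sign is also open: need-driven engagement could make delayed delivery look worse on raw scores, while regression to the mean among high-burden engagers could make it look better.
- Measuring the shift against d = 0.5 is tempting, but that figure is the plan's intervention-versus-control effect for Aims 1 and 2, not a timing benchmark.
- Engagement might also depend on patient survival or on remaining in care, but no passage says so. Section 4 (Missing Data) says participants are not dropped for these reasons. Only dependence on need is documented.
- Declining navigation is not the same as not engaging, because use of eSNAP alone counts as a level of the intervention.
- The 50% is an expected rate of giving data, in a passage about the path analysis. It is not an engagement rate, and 120 is not presented as the sample for the timing model. Discounting the 50% again for attrition would give a lower range, but would count non-completion twice.
- An offer-based contrast is not free of selection if non-engagers return no delayed-phase questionnaires; the selection then reappears as missing data.

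**Conclusion.** The asymmetry is in the plan's wording and no other section removes it. The early-versus-delayed contrast therefore carries selection on engagement in one arm, on a factor the plan itself links to need. Its size and direction cannot be known from the documents; 0.08 to 0.40 SD at 50% engagement and 0.02 to 0.10 SD at 90% are illustrations that rest on the assumed correlations of 0.1 to 0.5 and the normal selection model.

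The consequence is confined to one contrast in an aim labelled exploratory. The Week 8 primary test is not touched by this point.

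The Aim 3 path-analysis sample is a separate matter of figures: about 104 to 117 rather than at least 120, given about 2:1 allocation, 15% attrition applied once or twice to the intervention group, and half of the waitlist providing data. Because the plan gives 50% as a floor, a higher waitlist contribution would raise these totals.

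**What to change.** **Timing contrast (Section 4, Exploratory Aim 3)**

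- Make the main contrast offer-based among randomised caregivers: all waitlist caregivers offered delayed access versus those randomised to immediate intervention, leaving out the caregivers assigned without randomisation after V11.
- Adjust each side for the score at the start of its own 8-week period.
- Use the delayed-phase questionnaires already planned in Section 3b (Study Period), and state that they are sought from all offered waitlist caregivers whether or not they engage. State the missing-data assumption.
- If an engagers-only comparison is kept, label it supportive and apply the same definition, taken from the eSNAP and Navigator logs, to both arms.
- State whether non-engaging waitlist caregivers enter the model.

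**Aim 3 sample (Section 4, Sample size justification)**

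- Replace at least 120 with about 104 to 117 for the path analysis, and show the inputs.

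**Cost.** SAP wording and one re-specified exploratory model, plus the effort of pursuing questionnaires from waitlist caregivers who do not engage. The offer-based effect is diluted by non-engagers, and some delayed-phase outcomes will be missing. The randomised-only sample is smaller: if randomisation was 1:1, which is an assumption, about 53 + 53 = 106 caregivers, or 106 × 0.7225 ≈ 77 to 106 × 0.85 ≈ 90 after attrition at the plan's rate, and fewer if delayed-phase response is near 50%.

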Caregiving Characteristics will be assessed at baseline using purpose-designed questions about the patient/caregiver relationships, living arrangement, duration of caregiving, and weekly amount of caregiving. At Baseline, F1, and F2, caregiver activities will be assessed using modified versions of the Activities of Daily Living (Katz, Ford, Moskowitz, Jackson, & Jaffe, 1963) and Instrumental Activities of Daily Living (Lawton & Brody, 1969). The ADLs measure level of independence across six functions (bathing, dressing, going to toilet, transfer, continence and feeding) in chronically ill and aging populations. This version is a checklist of 8 activities associated with personal care to assess what the FCG helps the patient with because of their health status. IADLs assess the reason that the caregiver helps the patient with various activities (because of their health or not). We adapted it to administer to caregivers (to ask about what they help the patient with and why). The ADLs and IADLs have been validated in proxy for disabled populations (Andresen, Vahle, & Lollar, 2001).

FCG Well-Being

FCG burden will be assessed at baseline, F1, and F2 using the Zarit Burden Interview Short Form(Bedard et al., 2001), a 12-item widely-used measure of burden. Items are summed and higher scores reflect more burden. The scale has been validated in populations of advanced cancer FCGs and has very good internal consistency and discriminative ability (Higginson, Gao, Jackson, Murray, & Harding, 2010). The scale has also been used to identify changes over time (Gaugler, Mittelman, Hepburn, & Newcomer, 2010).

FCG distress will be assessed using the Generalized Anxiety Disorder (GAD-7) (Spitzer, Kroenke, Williams, & Löwe, 2006) and Patient Health Questionnaire (PHQ-8) (Kroenke et al., 2009) at baseline, F1, and F2.

FCG social support will be measured at baseline, F1, and F2 using the 8-item Duke-UNC Functional Social Support Questionnaire (Broadhead, Gehlbach, de Gruy, & Kaplan, 1988). Items are summed and higher scores reflect higher perceived social support. This multi-dimensional questionnaire is used in research to measure amount and type of social support, and used clinically to identify people at risk for isolation. The scale has been shown to be reliable(Broadhead, Gehlbach, deGruy, & Kaplan, 1989) and predictive of psychological and physical health outcomes (Bellon Saameno, Delgado Sanchez, Luna del Castillo, & Lardelli Claret, 1996).

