The number of network members entered into eSNAP will also be used as a measure of the size of the FCG social network. If participants use eSNAP over time, we will also capture change.

FCG social support and stress will be measured at baseline, F1, and F2 with Duke Social Support and Stress Scales (DUSOCS-SUP and DUSOCS-STR) (G. Parkerson, 2002). Within each subscale, respondents are prompted with specific family and non-family roles (e.g. significant other, children, neighbors) and asked to report the amount of support or stress provided by that relationship (no such person, none, some, a lot). DUSOCS has been shown to have good internal consistency and reliability, and excellent validity (J. G. Parkerson, Broadhead, & Tse, 1991; Parkerson Jr, Broadhead, & Chiu-Kit, 1992).

FCG coping and self-efficacy will be measured:

As a potential covariate at baseline, F1, and F2 using the Coping Self-Efficacy Scale (Chesney, Neilands, Chambers, Taylor, & Folkman, 2006), a 13-item measure of confidence in performing coping behaviors under stress. Items are summed within the scale's 3 factors: problem-focused coping, emotion-focused coping, and support from friends and family. Internal consistency and reliability are strong and scores are predictive of increased psychological well-being over time.

At Baseline, F1, and F2 using the Communication and Attitudinal Self-Efficacy Scale for Cancer (CASE-cancer) (Wolf, Chang, Davis, & Makoul, 2005). The original 12 items have been added upon to create a 19-item scale which measures three factors: understanding and participating in care, maintaining a positive attitude, and seeking and obtaining information.

Using the Caregiver Reaction Scale (Qualls & Williams, 2013) at baseline, F1, and F2. The Management of Meaning, Personal Gain, and Relational Deprivation subscales are used with minimal changes.

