We will also explore the dosing of the intervention. Because the intervention is needs-based, FCGs will receive different levels (e.g. eSNAP only; eSNAP plus Caregiver Navigator sessions of differing length/frequency). We will first describe the different levels of intervention used. We will then test the relationship of FCG reported support, distress, and burden and the frequency and time spent engaging in intervention components using repeated measures multilevel modeling. We hypothesize that FCGs who report less support or more distress or burden at enrollment will engage more components of the intervention.

Key mechanisms from the conceptual model (Figure 1) will also be explored using data from all who used the intervention at any time. Planned analyses include describing FCG health care utilization, determining whether intervention components (e.g. eSNAP visualization and resource list/Caregiver Navigator referrals) predict FCG health care utilization, and testing the relationship between FCG health care utilization and FCG well-being. We will also use path analysis to test mediation models mapping FCG support, burden, and distress over time and to test parallel processing models to determine interdependent effects between FCG and patient. For example, we will test whether change in FCG distress is associated with change in patient distress. In addition to identifying key mechanisms of the intervention, these analyses also would contribute to the literature describing the experience of FCGs of patients with a primary brain tumor, secondary (metastatic) brain tumor, or leptomeningeal disease over time.

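### The Aim 3 mechanism models are set in intervention users with no untreated contrast, so as specified they show that support, burden and distress move together, not that the intervention changed the mediator.

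*Combined protocol and SAP*

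**What the plan says.** In section 4 (Statistical Analyses), the Exploratory Aim 3 text says that the key mechanisms of the conceptual model "will also be explored using data from all who used the intervention at any time". In the same paragraph: "We will also use path analysis to test mediation models mapping FCG support, burden, and distress over time". No condition, exposure contrast or untreated comparator is named for these models. The worked example is an association between change in caregiver distress and change in patient distress. The paragraph closes by crediting these analyses with revealing how the intervention works.

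The sample-size paragraph of section 4 describes the path-analysis data. "The 80 participants in the intervention group will provide the primary data for these analyses", together with "additional data from participants in the waitlist control group who complete these assessments". It continues: "It is expected that at least 50% in this group will provide data", and concludes that "the expected sample size for the exploratory analyses will be at least 120".

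On the candidate mediators, section 3b (Questionnaires) states: "FCG social support will be measured at baseline, F1, and F2 using the 8-item Duke-UNC Functional Social Support Questionnaire". DUSOCS and the two self-efficacy scales follow the same schedule, and section 3b says caregiver questionnaires are collected from both groups at enrolment, week 4 (F1) and week 8 (F2). Network size is different: "The number of network members entered into eSNAP will also be used as a measure of the size of the FCG social network". Section 3a gives waitlist caregivers the intervention only after week 8, so they have no eSNAP entries in the control period.

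Section 3a also records that randomisation stopped after amendment V11. Later enrollees all receive the intervention, and about a 2:1 split is expected. Section 3b sets enrolment at 160 dyads.

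**The concern.** A mediation claim has two links: the intervention changes the mediator, and the mediator changes the outcome. If the model contains only people who used the intervention, and no exposure term, the first link is not in the model. What remains is an association among support, burden and distress over time. Section 2 of the protocol itself describes causes that could produce such an association without any intervention: rapid progression, physical debilitation, cognitive decline, and close interdependence of patient and caregiver outcomes.

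Aim 3 exists to inform later implementation. If co-movement is reported as mechanism, a successor trial could be built around a pathway that the intervention was never shown to affect.

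**Working it through.** **1. The plan's exploratory N.** Inputs from the sample-size paragraph: 80 intervention caregivers, and at least 50% of 80 waitlist caregivers. 80 + 0.50 x 80 = 120, so the figure reproduces. The same paragraph defines the 80 per group as completers of week 8. If untreated weeks 0-8 data were meant, the waitlist share would be 100% and the total 80 + 80 = 160. The 50% therefore fits waitlist caregivers who later take up the intervention, although the sentence does not say so.

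**2. The N under the modified design.** Inputs: 160 dyads, about 2:1, 15% attrition, half the waitlist contributing.
- 15% in total: 160 x 0.85 = 136, split 90.7 : 45.3; users = 90.7 + 0.5 x 45.3 = 113.
- 15% at each of two follow-ups: 160 x 0.85² = 115.6, split 77.1 : 38.5; users = 77.1 + 0.5 x 38.5 = 96.
- No attrition: 106.7 + 0.5 x 53.3 = 133.

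The 120 was not updated when the design changed.

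**3. Users-only association with no intervention effect.** The shared-cause correlation r between changes in support and burden is an assumption; the documents give none. Probability of p < 0.05 (two-sided), by Fisher z: Φ(atanh(r) x √(n − 3) − 1.96), the other tail being negligible.
- n = 120, r = 0.2: 0.2027 x 10.82 = 2.19, giving 59%.
- n = 120, r = 0.3: 0.3095 x 10.82 = 3.35, giving 92%.
- n = 120, r = 0.5: over 99%.
- n = 113, r = 0.2 and 0.3: 57% and 90%.

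**4. Two-arm comparison.** The joint test requires both arm-to-mediator and mediator-to-outcome (adjusted for arm) to be significant. With no arm effect and r = 0.3, 4,000 simulated trials gave 4.7% positive at 80:80 and 5.2% at 91:45. The ceiling of about 5% is set by the arm-to-mediator test.

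**5. Does the users-only result respond to a real effect on the mediator?** In the same simulation with a true shift of d = 0.5 in the mediator, the users-only association stayed at 92% (80:80). The arm-to-mediator test was significant in 88% at 80:80 and 78% at 91:45. The users-only result is the same whether or not the intervention moved the mediator.

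**6. What the two-arm model does not repair.** Let arm shift the mediator by d = 0.5, let the mediator have no effect on the outcome, and let the residual correlation be 0.2, 0.3 or 0.5. At 91:45 without baseline covariates, the joint test is still positive in about 48%, 74% and 78% of runs. Including arm does not remove mediator-outcome confounding.

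**7. Arm-to-mediator power, d = 0.5, two-sided 0.05.** Φ(0.5 / √(1/n₁ + 1/n₂) − 1.96).
- 90.7 : 45.3: 0.5 / 0.1819 = 2.75, power 0.78.
- 77.1 : 38.5: 0.5 / 0.1973 = 2.53, power 0.72 (0.71 by noncentral t).

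**The case against.** The strongest reply is that the text does not clearly exclude untreated data. The waitlist sentence in the sample-size paragraph comes just after mention of the 4- and 8-week assessments, which waitlist caregivers complete before treatment. This stands as an ambiguity. The 50% makes the users-only reading the better one, not a certain one.

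Second, exposure is not strictly constant among users. Waitlist caregivers who cross over have an untreated and then a treated period, and dose varies. This also stands, but no within-person contrast is specified for the mediation models. Dose is driven by need: the plan itself expects worse-off caregivers to engage more.

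Third, the percentages in steps 3 and 4 answer different questions. The 59% and 92% are not false-positive rates for the association, which is real by assumption; they show how often a real but non-causal association would be available to be read as a mechanism. That is correct and limits what the comparison proves. The simulations also treat the arms as exchangeable, although later enrollees were not randomised.

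Fourth, Aim 3 is labelled exploratory, and Aim 1 compares burden and distress between conditions, so a null there would be visible. This lowers the severity. It does not settle the mediator question, because support is not an Aim 1 outcome.

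A reader might also infer that eSNAP network size is a planned mediator that cannot be compared between arms. The lack of control-period values is real, but the mediation text names caregiver support, which has questionnaire measures, and never names network size.

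**Conclusion.** The point holds for the analysis as specified. The mechanism models, in the stated set and without an exposure contrast, cannot show that the intervention changed support or any other mediator, yet they are described as doing so. This conclusion follows from the structure of the model and does not depend on the assumed correlations. Those serve only to show that an association is likely to be found: about 59% to 92% of trials at n = 120 for r of 0.2 to 0.3, with no intervention effect.

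A reader might infer the stronger claim that this trial cannot estimate the path from intervention to mediator. The documents do not support that: support, stress and self-efficacy are scheduled in both groups at baseline, F1 and F2, so the path is estimable if waitlist weeks 0-8 are used. Nor would adding condition make the mediation result causal, as step 6 shows. The matter is one of specification and labelling in an exploratory aim, and should be corrected on that footing.

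**What to change.** - Fit the Aim 3 mediation models on baseline, F1 and F2 data from both groups. Use condition as exposure, F1 Duke-UNC, DUSOCS or self-efficacy as mediator, and F2 burden or distress as outcome, each adjusted for its baseline value.
- Adjust also for baseline patient function and the other measured confounders. The plan lists coping self-efficacy as a potential covariate; where it serves as mediator, its F1 value should not also be a covariate.
- Report a randomised-only sensitivity analysis, because enrollees after V11 were not randomised.
- State that the mediator-to-outcome path is observational, and add a sensitivity analysis for unmeasured mediator-outcome confounding.
- Keep the users-only, dose and network-size analyses, labelled as descriptive associations.
- Reconcile the sample-size paragraph with the Aim 3 text on whether untreated waitlist data enter, and restate the 120 for 160 dyads at about 2:1.

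The cost is SAP wording and one additional exploratory model on data already scheduled. The arm-to-mediator test has modest power for d = 0.5: about 0.78 with 15% total attrition, or 0.71-0.72 with 15% at each follow-up. The randomised-only analysis will have less.
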